8.6. Pharmacokinetics

Pharmacokinetic samples may be collected in cases of maladministration, liver events, to follow-up pregnancy, at plasma HIV 1 RNA retest of SVF, or as directed by the medical monitor.

Pregnant participants will have additional PK samples collected during the duration of the pregnancy. See Appendix 15: Information and Guidance for Managing Pregnant Participants

8.7. Pharmacodynamics

Pharmacodynamic parameters are not evaluated in this study.

8.8. Genetics

Genetics are not evaluated in this study.

8.9. Biomarkers

Biomarkers are not evaluated in this study.

8.10. Viral Genotyping and Phenotyping

Whole venous blood samples will be obtained from each participant to provide PBMCs and plasma for storage samples according to the Schedule of Activities Table (see Section 1.3) for potential viral genotypic and phenotypic analyses.

Genotypic and phenotypic analyses may be carried out by Monogram Biosciences using, but not limited to, their Standard PhenoSense and GenoSure testing methods for protease (PRO), reverse transcriptase (RT), and integrase assays.

8.10.1. HIV-1 Polymerase Viral Genotyping and Phenotyping

Participants meeting confirmed virologic failure will have plasma samples tested for HIV-1 PRO and RT genotype and phenotype and HIV-1 integrase genotype and phenotype from samples collected at the time of meeting suspected virologic failure; these results will be reported to the Investigator as soon as available to provide guidance for election of an alternative regimen.

8.11. Health Economics

Health Economics/Medical Resource Utilization and Health Economics parameters are not evaluated in this study.

9. STATISTICAL CONSIDERATIONS

9.1. Statistical Hypotheses

The hypotheses on the quantitative aspects of this study is that enhanced implementation strategy is superior than the standard implementation strategy in terms of mean staff study participant (SSP) AIM/IAM/FIM scores. i.e.,

 H_0 : μ (enhanced) = μ (standard) vs. H_1 : μ (enhanced) > μ (standard)

9.2. Sample Size Determination

The study size is based on practical considerations in terms of feasibility of enrolling an adequate number of sites on each implementation strategy balanced with the desire to have interventions tested across several types of investigative sites; as well as enrolling an adequate number of patient study participants in each site.

Approximately 24 sites (from feasibility process) will be selected from the feasibility process to achieve 18 sites randomly assigned to study implementation strategies and approximately 54 evaluable staff study participants for an estimated total of 27 evaluable study staff participants per implementation strategy group.

Assuming 10% screen failures, it is estimated that with 18 sites approximately 527 patient study participants will be screened to achieve 474 subjects enrolled and 450 evaluable patient study participants completing the study (assumes 5% of patient study participants would be non-evaluable) for an estimated total of 225 evaluable patient study participants per implementation strategy group.

Power to Show Superiority in mean SSP AIM/IAM/FIM scores

Table 10 shows preliminary AIM/IAM/FIM data from the ongoing U.S. implementation study CUSTOMIZE (209493).

	N	Mean	SD	Median	Observed Range (min-max)	Floor n (%)	Ceiling n (%)	Skewness	Kurtosis
AIM Scale (Total Sample)	24	4.39	0.61	4.13	3.25-5.00	0 (0.0%)	11 (45.8%)	-0.16	-1.58
IAM Scale (Total Sample)	24	4.45	0.59	4.50	3.25-5.00	0 (0.0%)	12 (50.0%)	-0.34	-1.39
FIM Scale (Total Sample)	24	4.32	0.71	4.25	3.00-5.00	0 (0.0%)	11 (45.8%)	-0.47	-1.09

Table 10Staff Study Participants Scores at Month 4 in CUSTOMIZE (209493)

Based on these preliminary data from CUSTOMIZE study, and the given sample size (the number of study participants), the power to detect a difference of 0.5 between the implementation arms in terms of AIM, IAM and FIM are shown in Table 11.

Table 11 Power to Detect a 0.5 Difference in AIM/IAM/FIM

Endpoint	ARM-S	ARM-E	Delta	SD	Alpha	N(S)	N(E)	Power*
AIM	4.39	4.89	0.5	0.61	0.05	27	27	84%
						36	36	93%

Endpoint	ARM-S	ARM-E	Delta	SD	Alpha	N(S)	N(E)	Power*
IAM	4.45	4.95	0.5	0.59	0.05	27	27	86%
						36	36	94%
FIM	4.32	4.82	0.5	0.71	0.05	27	27	72%
						36	36	84%

*Power calculation using two-sided t-test assuming equal variance.

As shown in Table 11, with 27 study staff participants (3 per site) surveyed on each arm, the study would have 72%-86% power to detect a 0.5 difference in FIM, AIM and IAM endpoints between ARM-E (Enhanced implementation strategy arm) and ARM-S (Standard implementation arm) assuming data from Table 10 (CUSTOMIZE study) for ARM-S.

And with 36 study staff participants (4 per site) surveyed on each arm, the study would have 84% - 94% power to detect a 0.5 difference in FIM, AIM and IAM endpoints between ARM-E and ARM-S.

Sample Size for Provider Population

An overall average number of 9 sites, per arm, would produces a two-sided 95% confidence interval with a distance from the mean paired difference (e.g. site level mean change from baseline in AIM, IAM or FIM score) to the limits (half-width) that is equal to 0.497 when the estimated standard deviation of the paired differences is 1.0, across sites.

Table 12Sensitivity Analysis for Sample Size versus Half-Width (Precision)-
Two-Sided 95% Confidence Interval (For Number of Sites)

[figure not shown]
Sample Size	Actual Distance from Mean		
	Difference to Lin	nits (Precision)	
	SD=0.5	SD=1.0	
10	0.358	0.715	
11	0.336	0.672	
12	0.318	0.635	
13	0.302	0.604	
14	0.289	0.577	
15	0.277	0.554	
16	0.266	0.533	
17	0.257	0.514	
18	0.249	0.497	
19	0.241	0.482	
20	0.234	0.468	

A sample size of 27 providers, per arm, produces a two-sided 95% confidence interval with a distance from the mean paired difference to the limits (half-width) that is equal to 0.396 when the estimated standard deviation of the paired differences is 1.0.

Table 13Sensitivity Analysis for Sample Size versus Half-Width (Precision)-
Two-Sided 95% Confidence Interval (for Number of Providers)

Sample Size	Actual Distance	from Mean
Campic Olze	Difference to Lin	
	SD=0.5	SD=1.0
21	0.228	0.455
22	0.222	0.443
23	0.216	0.432
24	0.211	0.422
25	0.206	0.413
26	0.202	0.404
27	0.198	0.396
28	0.194	0.388
29	0.190	0.380
30	0.187	0.373

[figure not shown]
Sample Size for Patient Population

A sample size of 225 patient subjects per implementation strategy group produces a twosided 95% confidence interval with a distance from the mean paired difference to the limits that is equal to 0.131 when the estimated standard deviation of the paired difference is 1.

Sample Size	Actual Distance Difference to Lin SD=0.5	
100	0.099	0.198
125	0.089	0.177
150	0.081	0.161
175	0.075	0.149
200	0.070	0.139
225	0.066	0.131
250	0.062	0.125

Table 14 Sensitivity Analysis for Sample Size versus Half-Width (Precision)-Two-Sided 95% Confidence Interval (for Patients)

Figure 7 Sensitivity Analysis for Sample Size versus Half-Width (Mean Diff to Limit) versus Sample Size - Patients (Multiple Confidence Levels)

As explained in other parts of this protocol, launching CAB LA + RPV LA in the real world may present challenges that were not observed in a clinical trial setting. Therefore, in addition to the primary analyses which focuses on study staff participants data, statistical analyses of patient outcome endpoints will be performed to evaluate changes in study patients' satisfaction score results, to allow a formal comparison between the two implementation strategies.

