6.3. Measures to Minimize Bias: Randomization and Blinding

For drug distribution purposes, the study will be single-arm, open-label study where all patients who pass screening will be assigned to CAB LA + RPV LA regimen.

For the purposes of implementation science/strategy, this study will be a two-arm study and sites will be either randomized to the Enhanced or Standard implementation strategy.

Cluster randomization will be applied because:

- Evaluation of intervention will be implemented at site level.
- For logistical convenience, and to avoid any contamination that could occur if implementation science interventions were provided for some subjects and not others within each site

Cluster randomization will be used to randomize sites in each country to either arm-e or arm-s. To achieve balanced implementation strategies across the sites, randomization may be stratified by clinic features. This will ensure data can identify whether a certain implementation strategy performs differently within a country or not, as well as between different countries.

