10.10. Appendix 10: Patient Study Participant Questionnaires

The following concepts are measured in the patient study participant questionnaires:

[figure not shown]
- Acceptability of the CAB+RPV injection (AIM)
- Appropriateness of the CAB+RPV injection (IAM)
- Feasibility of the CAB LA + RPV LA injection (FIM)
- Utility of patient specific toolkit resources
- CCI
- Facilitators and barriers to CAB LA + RPV LA related to time spent in appointments to receive the injections will be measured at Dose 1, 3, and 7.
- Preference

Acceptability, appropriateness, and feasibility will be measured by three brief 4-item measures (Weiner, 2017): the Acceptability of Intervention Measure (AIM), the Intervention Appropriateness Measure (IAM) and the Feasibility Intervention Measure (FIM). The AIM, IAM, and FIM access implementation outcomes identified in the Proctor Framework which are constructs of a 5-point Likert scale validated from the Proctor Framework. Reponses are measured using a 5-point Likert scale

Additional questions are included to evaluate facilitators and barriers from the patient perspective, and to evaluate the usefulness of the patient specific toolkit resources.

CCI	

Construct	Example Question
CCI	

Construct	Example Question
Outer	Context

Construct	Example Question
CCI	

Note: constructs are taken from the preparation and implementation phase. All constructs from implementation phase are noted with *.

CCI		

Construct	Example Questions
CCI	

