2.4.1.1. Power to Show Superiority in mean SSP AIM/IAM/FIM scores

Table A shows preliminary AIM/IAM/FIM data from the ongoing U.S. implementation study CUSTOMIZE (209493).

Table A Staff Study Participants Scores at Month 4 in CUSTOMIZE (209493)

	N	Mean	SD	Median	Observed Range (min-max)	Floor n (%)	Ceiling n (%)	Skewness	Kurtosis
AIM Scale (Total Sample)	24	4.39	0.61	4.13	3.25-5.00	0 (0.0%)	11 (45.8%)	-0.16	-1.58
IAM Scale (Total Sample)	24	4.45	0.59	4.50	3.25-5.00	0 (0.0%)	12 (50.0%)	-0.34	-1.39
FIM Scale (Total Sample)	24	4.32	0.71	4.25	3.00-5.00	0 (0.0%)	11 (45.8%)	-0.47	-1.09

Based on these preliminary data from CUSTOMIZE study, and the given sample size (the number of study participants), the power to detect a difference of 0.5 between the implementation arms in terms of AIM, IAM and FIM in line with our primary hypothesis are shown in Table B.

Table B Power to Detect a 0.5 Difference in AIM/IAM/FIM

Endpoint	ARM-S	ARM-E	Delta	SD	Alpha	N(S)	N(E)	Power*
AIM	4.39	4.89	0.5	0.61	0.05	27	27	84%
						36	36	93%
IAM	4.45	4.95	0.5	0.59	0.05	27	27	86%
						36	36	94%
FIM	4.32	4.82	0.5	0.71	0.05	27	27	72%
						36	36	84%

*Power calculation using two-sided T-test assuming equal variance.

As shown in Table B, with 27 study staff participants (3 per site) surveyed on each arm, the study would have 72%-86% power to detect a 0.5 difference in FIM, AIM and IAM endpoints between ARM-E (Enhanced implementation strategy arm) and ARM-S (Standard implementation arm) assuming data from Table A (CUSTOMIZE study) for ARM-S.

And with 36 study staff participants (4 per site) surveyed on each arm, the study would have 84% - 94% power to detect a 0.5 difference in FIM, AIM and IAM endpoints between ARM-E and ARM-S.

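### The IAM power row assumes an arm-e mean of 4.95 with SD 0.59, which a scale capped at 5.00 cannot produce, and every printed power ignores clustering of staff within randomised sites

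*Protocol*

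**What the plan says.** Protocol 9.2 takes the mean and SD of each staff scale from 24 staff in CUSTOMIZE (Table 10), adds 0.5 for arm-e, and states that "the power to detect a difference of 0.5 between the implementation arms in terms of AIM, IAM and FIM are shown in Table 11". The footnote reads "Power calculation using two-sided t-test assuming equal variance". The text concludes that at 27 per arm "the study would have 72%-86% power to detect a 0.5 difference in FIM, AIM and IAM endpoints between ARM-E" and ARM-S, "assuming data from Table 10 (CUSTOMIZE study) for ARM-S". It continues: "And with 36 study staff participants (4 per site) surveyed on each arm, the study would have 84% - 94% power to detect" the same difference. SAP 2.4.1.1 repeats the inputs and results in Tables A and B, giving "the power to detect a difference of 0.5 between the implementation arms in terms of AIM, IAM and FIM in line with our primary hypothesis".

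On the design, Protocol 6.3 states: "Cluster randomization will be used to randomize sites in each country to either arm-e or arm-s". Protocol 9.2 plans 9 sites per arm, with 3 or 4 staff per site. Neither power table contains an ICC, a design effect or site-level degrees of freedom. Protocol 9.4 mentions accounting for site only for patient data.

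**The concern.** Table 10 shows a maximum of 5.00 on each scale, with 11, 12 and 11 of 24 staff at the ceiling for AIM, IAM and FIM. Moving the mean up by 0.5 pushes arm-e against that ceiling, where there is little room left for spread. Keeping the same SD may then describe a distribution that cannot exist. IAM has the least room: its planned mean is 0.05 below the cap.

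The IAM row matters because it sets the upper end of both ranges quoted in the text. Those ranges are the only power statements for the study's only formal hypothesis.

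A second, separate matter affects all three rows. Staff at one site share a clinic, its leadership and its allocated strategy, so their scores may be correlated. A t-test on 27 or 36 independent staff per arm gives no allowance for that.

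**Working it through.** **1. Reproducing the plan.** Inputs from Table 11: difference 0.5; SD 0.61 (AIM), 0.59 (IAM), 0.71 (FIM); two-sided alpha 0.05; n = 27 or 36 per arm. The noncentrality is 0.5 / (SD × √(2/n)), with 2n − 2 df. For IAM at 27: 0.5 / (0.59 × √(2/27)) = 3.11, critical t 2.007, power 86.3%.

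| | 27 per arm (stated) | 36 per arm (stated) |
|---|---|---|
| AIM | 84.0% (84%) | 92.9% (93%) |
| IAM | 86.3% (86%) | 94.4% (94%) |
| FIM | 71.9% (72%) | 83.8% (84%) |

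All six agree, so the method is identified and the printed arithmetic is right.

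**2. The bound.** For scores between L and 5 with mean m, the largest SD is √((5 − m)(m − L)).

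- IAM, m = 4.95, L = 1: √(0.05 × 3.95) = 0.444. With L = 0: √(0.05 × 4.95) = 0.497. Both are below 0.59.
- At SD 0.59 and L = 1, the highest attainable mean is 4.911, a difference of 0.461 from 4.45.
- AIM, m = 4.89, L = 1: √(0.11 × 3.89) = 0.654, above the assumed 0.61. Possible.
- FIM, m = 4.82, L = 1: √(0.18 × 3.82) = 0.829, above the assumed 0.71. Possible.
- To have the assumed SD, the lowest arm-e score must be at or below m − SD²/(5 − m). This is 1.51 for AIM and 2.02 for FIM, against CUSTOMIZE minima of 3.25 and 3.00. For IAM it is −2.01, which is off the scale.

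**3. Power at 0.5 on the bounded scale, staff independent.** Arm-s scores were drawn from the one set of 24 quarter-point scores that matches every Table 10 statistic for each scale:

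- IAM: 3.25×1, 3.50×1, 4.00×10, 5.00×12.
- AIM: 3.25×1, 3.50×1, 3.75×3, 4.00×7, 4.25×1, 5.00×11.
- FIM: 3.00×2, 3.25×1, 3.50×1, 3.75×2, 4.00×5, 4.25×2, 5.00×11.

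Arm-e scores were either 5 or a low value a, with proportion (5 − m)/(5 − a) at a. The same t-test was applied.

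| | Low value a | Arm-e SD | 27 / 36 per arm |
|---|---|---|---|
| IAM | 1 (largest attainable SD) | 0.444 | 86% / 93% |
| IAM | 3.25 | 0.292 | 97% / 99% |
| AIM | 1.51 (plan's SD) | 0.61 | 79% / 88% |
| AIM | 3.25 | 0.425 | 92% / 97% |
| FIM | 2.02 (plan's SD) | 0.71 | 70% / 80% |
| FIM | 3.00 | 0.572 | 78% / 88% |

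These figures are approximate. The first row of each pair is a limiting case. For IAM with a = 1, only 0.05/4 = 1.25% of arm-e staff score 1 and everyone else scores 5. About 71% of 27-person samples would then be all at 5 (0.9875^27).

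**4. Clustering, table SDs kept.** The design effect is 1 + (k − 1) × ICC, with k = 3 or 4 staff per site. Replace n by n divided by the design effect, with 18 − 2 = 16 df (critical t 2.120). The ICC is an assumption. For FIM at 27 and ICC 0.20, the design effect is 1.4, effective n is 19.3, noncentrality is 2.19 and power is 54%.

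| | 27 per arm, ICC 0.05 to 0.20 | 36 per arm, ICC 0.05 to 0.20 |
|---|---|---|
| AIM | 77% to 67% | 86% to 73% |
| IAM | 80% to 70% | 88% to 76% |
| FIM | 64% to 54% | 74% to 60% |

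Part of the loss comes from the 16 df alone: at ICC 0 and 27 per arm the same formula gives 81%, 83% and 68%.

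**The case against.** **The impossible row may do no harm.** A reader might infer from the ceiling that power is overstated. The documents do not support that. At a fixed 0.5 difference the cap forces a smaller arm-e SD, and IAM power comes out about equal to the plan's or higher. Nor is AIM shown to be overstated: 79%/88% rests on one extreme shape, with about 3% of arm-e staff near 1.5 and the rest at 5. Scores kept within the CUSTOMIZE range give 92%/97%, and the printed 84%/93% lies between the two. This objection stands in full as to direction. It does not make the IAM inputs possible.

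**The floor is assumed.** The floor of 1 and the quarter-point step are inferred from the patient questionnaire appendix ("Acceptability, appropriateness, and feasibility will be measured by three brief 4-item measures", on a five-point Likert scale); the staff instrument is not visible. That limits the AIM and FIM shapes. The IAM row fails with a floor of 0 as well.

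**0.59 could be a pooled SD.** With arm-e at most 0.444, arm-s would need at least √(2 × 0.59² − 0.444²) = 0.706. The text takes Table 10 for arm-s, which is 0.59.

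**The clustered figures are not a correction.** No ICC is given, and step 4 keeps the table SDs, including the unattainable one. Bounded shapes can give more. A simulation with arm-e held closer to the ceiling (SD 0.32, 0.21 and 0.42), tested on site means, gave AIM 93%-88%, IAM 97%-94% and FIM 81%-75% at 27 per arm over the same ICC range. So no single clustered range can be offered as the right one. This stands.

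**The staff analysis is elsewhere.** SAP 2.4 defers it to a separate plan, which may model site. No analysis fault can be inferred. That plan cannot change the powers printed here.

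**Conclusion.** Wrong as written, as a planning assumption. The IAM row of Protocol Table 11 and SAP Table B needs an SD of 0.59 where the scale allows at most 0.444 (floor 1) or 0.497 (floor 0). The 86% and 94% that close the quoted ranges therefore describe a scenario that cannot occur. This rests only on the 5.00 cap and the printed inputs.

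The ceiling by itself does not establish a direction of error. Bounded-scale power at 0.5 depends on the arm-e shape, and the plan states none.

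Separately, all six powers assume independent staff in a design that randomises sites. Any positive within-site correlation lowers power relative to the same calculation without it. How far depends on an ICC the documents do not supply, so the step 4 figures illustrate the size and do not replace the printed values.

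**What to change.** In Protocol 9.2 and SAP 2.4.1.1:

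- Replace the IAM row with an arm-e mean and SD that a scale capped at 5.00 allows.
- State the assumed arm-e distribution for AIM, IAM and FIM, and compute power from it.
- Restate the 72%-86% and 84%-94% ranges with an allowance for staff clustered within sites, over a stated ICC range, and label the ICC as an assumption if no source exists.

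The cost is recalculation and table wording in two sections. The sample size rests on feasibility and stays as it is. The downside is that some stated powers will look less favourable.

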For SSPs, the study is two-arm, unblinded, non-interventional and cluster-randomized at the country level. Sites within a given country will be randomized to either the Standard (Arm-s) or the Enhanced (Arm-e) implementation arm. The two arms will involve the provision of overlapping but distinct types of implementation components that are designed to assist in the local implementation of the study drug at each site. Arm-s represents the traditional provider support by a medical science lead and product materials. Arm-e models a higher level of provider support with added face to face meeting, trainings, and additional touchpoints for administration of CAB LA + RPV LA. The study will evaluate both qualitative and quantitative measures across arm, clinic type, provider type, and country to determine the most effective implementation strategies and to identify barriers and facilitators (including solutions). Clinical data will be collected to monitor safety and efficacy.

Objectives and Endpoints:

Objectives	Endpoints
Primary	
Staff Study Participants (SSP):To evaluateacceptabilityappropriatenessfeasibility	Quantitative Change of Acceptability of Implementation Measure (AIM) Score, Implementation Appropriateness Measure (IAM) Score, Feasibility of Implementation Measure (FIM) Score over time assessed quantitatively via questionnaires through Month 12. ^a
	Qualitative Semi-structured interviews (SSI) assessed qualitatively through Month 12.
Secondary	
 Staff Study Participants: To evaluate Facilitators to implementation Barriers to implementation Adaptations/Modifications to address barriers and facilitators 	Quantitative:Change of Implementation Leadership Scale(ILS), Change of Implementation Climate Scale(ICS) over time assessed quantitatively viaquestionnaires through Month 12.ªSummarize components from EnhancedImplementation & Standard Implementation:• FRAME-IS outcome Months 2 – 12(monthly)Summarize components from EnhancedImplementation:• CQI 1-hour calls/PDSAs minimum of Months 2-7 (monthly)
 Patient Study Participants (PSP) To evaluate Facilitators to implementation 	Qualitative SSIs assessed qualitatively through Month 12. Quantitative: Questionnaires assessed quantitatively through Dose 7. ^b

Objectives	Endpoints

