Dosing	
 • Intervention Phase^o Open-label in respect to treatment; • Site Randomization: Intervention Phase: Site Randomization 1:1 to ARM-E: ARM-S
Time & Events	
 • Refer to Appendix 1: Schedule of Activities
Treatment Assignment	
 • CAB LA+RPV LA (N=450)
Interim Analysis	
 • Interim analyses will be conducted at two timepoints: 1) when 50% of subjects have received their 3rd injection and 2) when 100% of subjects have received their 3rd injection. • The primary analysis will be conducted at Month 12

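### Power for the primary staff AIM/IAM/FIM comparison treats staff as independent, although sites are the randomised unit

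*Protocol*

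**What the plan says.** Randomisation is by site. Protocol 1.1 says "Sites within a given country will be randomized to either the Standard (Arm-s) or the Enhanced (Arm-e) implementation arm", Protocol 6.3 says "Cluster randomization will be used to randomize sites in each country to either arm-e or arm-s", and SAP 2.3 gives "Site Randomization 1:1 to ARM-E: ARM-S". Protocol 9.2 expects 18 randomised sites and about 54 staff, so about 9 sites and 27 staff per arm.

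The one formal hypothesis, in Protocol 9.1, is that the "enhanced implementation strategy is superior than the standard implementation strategy in terms of mean staff study participant (SSP) AIM/IAM/FIM scores"; the alternative is written as one-sided.

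Protocol 9.2 then states that "with 27 study staff participants (3 per site) surveyed on each arm, the study would have 72%-86% power to detect a 0.5 difference", and continues "And with 36 study staff participants (4 per site) surveyed on each arm, the study would have 84% - 94% power". The footnote to Table 11 reads "Power calculation using two-sided t-test assuming equal variance"; the footnote to SAP Table B reads "Power calculation using two-sided T-test assuming equal variance". Neither section mentions an ICC, a design effect or site-level degrees of freedom.

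On analysis, Protocol 9.4 says in words that patient data will account for nesting in sites. It labels staff data as site-level and says each outcome will be handled accordingly. Protocol 9.4.1 says only that mean scores will be compared between arms with p-values. SAP 2.4 and 7 defer the detail to a separate Evidera SAP, which was not supplied.

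**The concern.** Staff at one site share a clinic, its leadership and the same implementation support. If their scores are correlated, 27 staff in 9 sites carry less information than 27 independent people, and the between-arm comparison has about 16 degrees of freedom rather than 52. A power figure that ignores this is too high for an unadjusted comparison that respects the randomisation.

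This power supports the trial's only formally stated hypothesis. It was added to the protocol at the request of an ethics committee (Protocol Appendix 17). If the enhanced arm shows no advantage, that result will be read against 72% to 94% power.

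Two inputs are also unclear. The alternative in 9.1 is one-sided but the power is two-sided. The SD comes from Month 4 scores in another study, whereas 9.4.1 labels the endpoint as change from baseline at Month 12 and then describes a comparison of mean scores.

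**Working it through.** **Inputs** (Protocol 9.2, Tables 10 and 11; SAP Tables A and B). Difference 0.5; SD 0.61 (AIM), 0.59 (IAM), 0.71 (FIM); alpha 0.05; n = 27 or 36 staff per arm, that is m = 3 or 4 in each of 9 sites per arm.

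**Step 1: reproduce the printed figures.** For independent staff, SE = SD × √(2/n), noncentrality = 0.5/SE, df = 2n − 2. For AIM with n = 27: SE = 0.61 × √(2/27) = 0.166, noncentrality 3.01, df 52, power 84.0%. All results:

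| | AIM | IAM | FIM |
|---|---|---|---|
| 27 per arm, computed | 84.0% | 86.3% | 71.9% |
| 27 per arm, printed | 84% | 86% | 72% |
| 36 per arm, computed | 92.9% | 94.4% | 83.8% |
| 36 per arm, printed | 93% | 94% | 84% |

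All six agree. A one-sided test at 0.05 with 27 per arm gives 90.8/92.3/81.8%, which does not match.

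**Step 2: allow for site.** The SE is multiplied by √(1 + (m − 1) × ICC), and df = 18 − 2 = 16. For AIM with m = 3 and ICC 0.10: design effect 1.2, SE = 0.166 × √1.2 = 0.182, noncentrality 2.75, power 73.3%. The documents give no ICC, so the values below are assumptions (two-sided 0.05, AIM/IAM/FIM):

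| ICC | 3 per site | 4 per site |
|---|---|---|
| 0 | 81/83/68% | 90/92/80% |
| 0.05 | 77/80/64% | 86/88/74% |
| 0.10 | 73/76/60% | 82/84/69% |
| 0.20 | 67/70/54% | 73/76/60% |

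At ICC 0.10 the loss is 10 to 12 points with three per site and 10 to 15 with four. With staff-level df kept (52), three per site and ICC 0.10, power is 77/80/64%. So about 7 to 8 points of that loss come from the design effect and just under 4 from the degrees of freedom.

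**Step 3: sidedness.** One-sided at 0.05, three per site: independence gives 91/92/82%; ICC 0.10 with 16 df gives 84/86/73%. The loss is 6 to 9 points.

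**Step 4: baseline adjustment.** The variance is also multiplied by 1 − ρ², with 15 df. At ICC 0.10 and ρ = 0.5: 84/87/72% with three per site, 91/93/81% with four. At ρ = 0.3 and three per site: 77/80/64%.

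**Step 5: ceiling check on IAM.** If scores run from 1 to 5 (an assumption; Protocol 10.10 says only a 5-point scale), a mean of 4.95 allows an SD of at most √(0.05 × 3.95) = 0.44, below the 0.59 used. With 0.59 in the standard arm and 0.44 in the enhanced arm, 27 per arm, IAM power is about 93% under independence and about 86% at ICC 0.10 with 16 df. The level changes; the loss from clustering remains.

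**Step 6: type I error, only if the staff test proves to be the individual-level t-test.** Simulation at ICC 0.10 gives a two-sided error of about 7.4% (three per site) or 8.6% (four per site), against a nominal 5%.

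**The case against.** The strongest reply is that nothing in Table 11 is miscalculated. The sample size rests on feasibility, and the staff analysis sits in a plan that was not supplied and may well model site. Any loss depends on an ICC that no document provides and on a choice of 16 degrees of freedom that no document fixes. With staff-level degrees of freedom, an ICC up to roughly 0.015 would leave all six figures within two points. With a baseline correlation of 0.5, the row for three per site is fully recovered at ICC 0.10. Read one-sided, the site-level figures at ICC 0.10 are close to print. Randomising within country, perhaps stratified by clinic features, could also help. Protocol Table 12 shows that site was recognised as a unit.

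Much of this is fair about size. The loss is a range, not a number, and whether the staff analysis accounts for site is an open question rather than a shown error. But none of it supports the printed figures. The stated calculation claims no baseline correlation, and one cannot be presumed: Protocol 4.2.5 asks staff about expectations at Month 1 and about experience later. No gain from stratification is quantified. The one-sided reading contradicts the tables' own footnotes. Table 12 gives confidence-interval half-widths for paired change, not between-arm power. If the Evidera SAP does model site, Tables 11 and B describe a different test from the planned one.

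**Conclusion.** The concern holds. The arithmetic is right for independent staff, but that assumption does not fit a trial that randomises about 18 sites, so the stated 72–86% and 84–94% are not the power of an unadjusted site-respecting comparison. At an assumed ICC of 0.10 with 16 df, two-sided, the figures are about 60–76% with three staff per site and 69–84% with four. The size rests on the assumed ICC, equal site sizes, the SDs borrowed from the other study, and no baseline adjustment. The direction for an unadjusted comparison does not depend on the value: power is already slightly lower at ICC 0 with site-level df, and any positive ICC lowers it further. Baseline adjustment could offset the loss, fully or partly, only if a useful correlation is assumed and stated. Because this is the stated power for the primary comparison, it should be corrected.

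**What to change.** 1. Restate Protocol Table 11, SAP Table B and the two power sentences over a stated ICC range, with degrees of freedom that match the planned model. Say whether the SD refers to the Month 12 score, the change or the baseline-adjusted score, and give any baseline correlation assumed. Reconcile the one-sided alternative in 9.1 with the two-sided test in 9.2.
2. State in Protocol 9.4.1 that the staff between-arm comparison accounts for site, either by a random site effect with small-sample degrees of freedom or by site means. State also that it adjusts for a baseline score taken before enhanced-arm support begins; Table 2 sets no order between the first SWAT meeting and the Month 1 questionnaire. If the Evidera SAP already specifies this, cite it.
3. Note that the half-widths for providers (0.396 at n = 27) and patients (0.131 at n = 225) also assume independence. Any restatement should use an ICC for change scores and site-level degrees of freedom.

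The cost is wording and recalculation. No participants are added, because the sample size is set on feasibility. The stated power will look less favourable unless a baseline correlation is assumed and declared.
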